1.3 Schedule of Activities (SoA)

Table 1 Schedule of Activities

| Procedures | Screening and Baseline PSG ¹ | | Blinded baseline placebo, at-home dosing | Treatment Period | | | Visit 5 EOS ² | Notes |
|---|--|--|--|---|----------------------|---------------------------|-----------------------------|---|
| | Non-PSG Daytime Visit 1 | PSG night and next morning, Visit 2 | | Double- blind study treatment, at-home Dosing | Daytime Visit 3 | Visit 4 PSG Visit | | |
| Trial Day (Visit Window) | -28 to -1 | -7 to -1³ | 1 to 2⁴ | 3 – 11 ± 2⁵ | 6⁶ | 12 ± 2⁷ | 26 ± 4 | |
| Pre-screening | X ⁸ | | | | | | | Determination of basic eligibility for the study |
| Informed consent ⁹ | X | | | | | | | |
| Consent for genetic testing for CYP2D6 | X | | | | | | | |
| Inclusion and exclusion criteria | X | | | | | | | |
| Demography | X | | | | | | | |
| STOP-Bang Questionnaire | X | | | | | | | Only used for participants without a history of diagnosis of OSA or CPAP use |
| Physical exam | X | | | | | | | |
| Medical and surgical history | X | | | | | | | Includes drug and substance usage and psychiatric history |
| Blood sample for CYP2D6 genotype | X | | | | | | | |
| Serum pregnancy test (WOCBP only) | X | | | | | | X | |

| | | | | | | | | |
|---|---|---|---|---|--|---|---|--|
| Urine drugs of abuse ¹⁰ testing, ethanol testing | X | | | | | | | |
| Randomization | | X | | | | | | Randomization takes place the morning after PSG testing for participants that qualify |
| Medication distribution to participant, and study instructions and device | | X | | | | | | Prior to discharge morning after PSG |
| QHS self-administration of baseline placebo | | | X | | | | | 2 nights of QHS placebo, at home, all participants; administer ~30 minutes prior to bedtime |
| International Prostate Symptom Scale | X | | | | | | | Male participants only |
| QHS administration of randomized study treatment (combination drug or placebo) | | | | X | | X | | Total of 10 nights: 3 nights low dose (25 mg atomoxetine/ 1.5 mg oxybutynin) followed by 7 nights randomized study treatment for participants randomized to active drug; 10 nights placebo for participants randomized to placebo. |
| “Reminder” telephone call/message | | | | X | | | | Day 10±2, participants reminded about study procedures and upcoming PSG visit ¹¹ |
| Clinical laboratory assessments (hematology, clinical chemistry and urinalysis) | X | | | | | X | X | |
| 12-lead ECG | X | | | | | | X | |

| | | | | | | | | |

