4.1 Overall Design

This is a randomized, double blind, placebo-controlled, repeat-dose, parallel arm, outpatient and inpatient, multi-center, dose finding study of the combination of atomoxetine and oxybutynin in adults with OSA documented by PSG. Approximately 140 participants will be randomized equally to receive 1 of 3 different fixed-dose combinations of oxybutynin and atomoxetine, or matching placebo. For all participants, there is an initial 2-night at-home blinded baseline period in which placebo is dosed. Following this baseline placebo period, participants randomized to the 3 study treatment arms receive 3 nights of a low-dose run-in of the combination, consisting of atomoxetine 25 mg/oxybutynin 1.5 mg. In contrast, during this 3-night run-in period, participants randomized to placebo receive placebo. Following this 3-night run-in period, participants will receive the treatment to which they were randomized, i.e., 1 of the 3 different fixed-dose combinations of drug, or placebo. Overall study duration will be up to 8-9 weeks. Dosing of the study treatment will occur approximately 30 minutes prior to bedtime. Participants who withdraw from the study will not be replaced.

Study participants will undergo eligibility screening that will include an initial exam to determine whether non-PSG enrollment criteria are met, followed by a 1-night inpatient PSG test for participants who qualify based on non-PSG criteria. For participants who are eligible and enroll in the study, the screening PSG night will serve as the baseline measure for AHI and other PSG efficacy and safety endpoints. Baseline measures for additional secondary and tertiary endpoints based on home oximetry will be recorded at home during the placebo period, and these endpoint measures will continue to be collected over the subsequent at-home study treatment dosing period. On the final night of dosing, participants will return for inpatient PSG. The primary efficacy endpoint is the proportion of participants with $\geq 50\%$ reduction in AHI from screening/baseline to final day of treatment with study treatment (study Day 12 \pm 2).

Participants will return 2 weeks after the last dose for an EOS Visit ([Figure 2](#)). No subsequent open-label extension is planned following the study.

Figure 2: Overview of Study Design

Abbreviations: ATO = atomoxetine; EoS = end of study; OXY = oxybutynin; PSG = polysomnography.

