4.3 Justification for Dose

The high-dose AD036 in this study is atomoxetine 75 mg/ oxybutynin 5 mg, similar to the dose used in initial human studies (atomoxetine 80 mg/oxybutynin 5 mg). To explore the potential efficacy and safety of lower atomoxetine and oxybutynin doses, the following 2 additional dose arms will be studied: atomoxetine 75 mg/oxybutynin 1.5 mg and atomoxetine 25 mg/oxybutynin 5 mg.

Prescribing information for atomoxetine specifies at least 3 days of dose escalation prior to dosing >40 mg. This study incorporates a 3-day dose escalation period using atomoxetine 25 mg/oxybutynin 1.5 mg for participants assigned to active drug in the randomized dosing

period. Participants assigned to placebo in the randomized dosing period will correspondingly be dosed with placebo in the 3-day dose escalation period.

Prior to the dose escalation period all participants will be assigned to 2 days of placebo to establish baseline measures.

A detailed description of the chemistry, pharmacology, efficacy, and safety of AD036 is provided in the Investigator's Brochure.

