All statistical tests of hypotheses will be two-sided and will employ a level of significance of $\alpha = 0.05$.

1. 75/1.5 dose arm vs Placebo arm
2. 25/5 dose arm vs Placebo arm
3. 75/5 dose arm vs. 75/1.5 dose arm
4. 75/5 dose arm vs. 25/5 dose arm
5. 75/1.5 dose arm vs 25/5 dose arm

Oxygen desaturation index, low-dose run in (25/1.5) vs. placebo, or vs 75/5 final dose, at-home nights

The oxygen desaturation index is the average number of oxygen desaturations 4% or more below the baseline level per hour of sleep.

Proportion of patients with $\geq 50\%$ improvement in Oxygen desaturation index will be presented for the following comparisons:

1. Within the 75/5 dose arm, proportion of ODI responders in 75/5 dose period vs proportion of ODI responders 25/1.5 low dose run-in period. The responders in 75/5 dose period will be calculated from average of 2 baseline nights to average of 6 treatment nights and the responders in 25/1.5 dose period will be calculated from average of 2 baseline nights to average of 3 run-in nights.
2. For all 3 active arms combined (i.e. 75/5;75/1.5;25/5) proportion of ODI responders in 25/1.5 low dose run-in period vs proportion of ODI responders in placebo period. The responders will be calculated from average of 2 baseline nights to average of 3 run-in nights and then the comparison will be done between combined active treatments vs placebo.

Estimate of the odds ratio along with associated 95% Wald confidence interval (CI) and two-sided p-value will be presented

All statistical tests of hypotheses will be two-sided and will employ a level of significance of $\alpha = 0.05$.

Proportion of apneas to hypopneas

Proportion of apneas to hypopneas is defined as = $H/(A+H)$.

Where,

A-Number of Apnea with onset during TST

H-Number of Hypopnea with onset during TST

This variable will be derived for each individual subject at both PSG visit (Visit 2 and Visit 4)

Change from baseline in the proportion of apneas to hypopneas at second PSG visit (visit 4) will be compared between 75/5 dose and placebo group using ANCOVA with treatment group as factor and baseline results as a covariate.

Adjusted means, Standard error (SE) of Adjusted means, 95% confidence intervals, within treatment p-values for each treatment group, treatment group difference, 95% confidence interval of the difference and the between-treatment p-values based on the statistical model described above will also be presented

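### The exploratory ODI comparison of 75/5 with the 25/1.5 run-in uses one arm in a fixed order, so non-drug change over time is mixed with the dose step, although placebo is recorded in the same two windows.

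*SAP*

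**What the plan says.** The ODI entry in SAP 4.9.4 (Tertiary/Exploratory Variables) defines two comparisons. The first is "Within the 75/5 dose arm, proportion of ODI responders in 75/5 dose period vs proportion of ODI responders 25/1.5 low dose run-in period". Treatment-period responders are "calculated from average of 2 baseline nights to average of 6 treatment nights", and run-in responders are "calculated from average of 2 baseline nights to average of 3 run-in nights". The second pools the three active arms and compares them with placebo over the run-in nights only. An odds ratio, a 95% Wald interval and a two-sided p-value at 0.05 are specified for this entry. No paired method is named.

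The order of periods is fixed. The Schedule of Activities in Protocol 1.3 gives "3 nights low dose (25 mg atomoxetine/ 1.5 mg oxybutynin) followed by 7 nights randomized study treatment for participants randomized to active drug", and "10 nights placebo for participants randomized to placebo". Protocol 4.1 says that the active arms all "receive 3 nights of a low-dose run-in of the combination, consisting of atomoxetine 25 mg/oxybutynin 1.5 mg", while "during this 3-night run-in period, participants randomized to placebo receive placebo". The same schedule has the oximeter worn on every at-home dosing night in every arm.

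The Protocol's own exploratory endpoint for these nights is ODI in the run-in against baseline. The run-in versus 75/5 contrast appears only in the SAP.

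**The concern.** Within a single arm, the change from Days 3-5 to Days 6-11 is both a dose change and a passage of time. Adaptation to the oximeter, the ordinary night-to-night course, and any slow return from an unrepresentative two-night baseline would all enter the odds ratio beside the dose step. A correctly paired test would not help. It would fix the standard error and leave the confounding in place.

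The trial has a concurrent control for this. Placebo participants are recorded through both windows with no dose change, yet the contrast does not use them. The secondary ODI analysis in SAP 4.9.3 compares all arms, but only over the six treatment nights. The second comparison in 4.9.4 uses placebo, but only over the three run-in nights. The change from one window to the other is never compared between arms.

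What is at stake is modest but real. This is the only planned comparison of 25/1.5 with a higher dose, in a trial meant to inform dose selection. Drift could make 75/5 look better than the run-in dose with no dose effect, or could hide a real one.

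**Working it through.** The documents state no figure for this contrast and give no ODI drift or ODI variability. The arithmetic below therefore shows sensitivity under stated assumptions and does not estimate the bias.

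**Inputs from the documents.** Two baseline nights, three run-in nights and six treatment nights; a responder has an ODI at or below half of baseline; 35 participants per arm.

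**Assumptions.** Run-in ODI averages a ratio r of baseline. On the log scale, the between-person SD is 0.30 and the night-to-night SD s is 0.25 or 0.35. There is no effect of 75/5 beyond 25/1.5. A drift d multiplies r by (1 − d) in the treatment window.

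**Formula.** With k nights in the window,

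P(responder) = Φ( (ln 0.5 − ln r) / √(0.30² + s²(1/k + 1/2)) ).

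For r = 0.65, s = 0.25 and k = 3, the denominator is √(0.0900 + 0.0625 × 0.8333) = 0.377 and the numerator is −0.262, so P = Φ(−0.696) = 24.3%. For the treatment window with d = 10%, r = 0.585 and k = 6. The denominator is 0.363, and P = Φ(−0.433) = 33.3%. The gain is 9.0 points.

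| Run-in ratio | s | Run-in responders | No drift | 10% drift | 20% drift |
|---|---|---|---|---|---|
| 0.65 | 0.25 | 24.3% | 23.5% | 33.3% | 45.7% |
| 0.65 | 0.35 | 27.5% | 26.3% | 35.2% | 46.2% |
| 0.80 | 0.25 | 10.6% | 9.8% | 15.8% | 24.8% |
| 0.80 | 0.35 | 14.2% | 12.8% | 18.9% | 27.6% |
| 0.90 | 0.25 | 6.0% | 5.3% | 9.2% | 15.8% |
| 0.90 | 0.35 | 9.0% | 7.8% | 12.2% | 18.9% |

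Matched by s, the false gain at r = 0.65 is about 8-9 points for 10% drift and 19-21 points for 20% drift. At r = 0.80-0.90 and 10% drift it is about 3-5 points. The no-drift column isolates the effect of averaging three nights against six. It is about 1 point, and it works against 75/5.

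**Rejection rates.** A simulation used 35 per arm and 6,000 trials per setting, with run-in ODI effects of 30-50%, night-to-night log SD 0.25-0.40, between-person log SD 0.40, the same drift in every arm and no dose step.

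| Drift | Within 75/5, exact McNemar | Within 75/5, Wald odds ratio, periods treated as independent |
|---|---|---|
| 0% | 0.4-1.7% | 0-0.2% |
| 10% | 3-10% | 0.5-0.9% |
| 20% | 27-61% | 9-22% |
| 30% | 79-97% | 49-77% |

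At 20% drift the apparent odds ratio is 1.8-2.2.

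**Which control works.** The unadjusted 75/5-minus-placebo difference in the change in log ODI rejects in 4.7-5.5% of trials at every drift from 0 to 30%. Subtracting placebo on the responder-proportion scale does not work: it rejects in 22-78% of trials at 20% drift. Few placebo participants are near the 50% threshold, so the same drift moves few of them across it. The controlled analysis therefore has to be on the continuous scale.

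**The case against.** The strongest reply is about consequence. The endpoint is exploratory and unranked, and the SAP makes no causal dose claim from it. The 25/1.5 dose is a three-night escalation step, not a randomized arm. Drift of 10-20% within a few nights is assumed. At 10% drift a false positive is uncommon: about 3% or less with the Wald odds ratio and at most about 11% with McNemar, over the assumption sets tried. Placebo responder rates in both windows will be visible, from the second comparison in 4.9.4 and the secondary ODI analysis. All of this stands and limits the importance of the point. It does not supply a control: placebo rates printed elsewhere do not correct a p-value computed in one arm, and the responder scale is a poor place to make the correction by eye.

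A reader might infer three stronger things that the documents do not support.

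- **That the analysis is shown to favour 75/5.** No drift figure is given, and drift could run either way.
- **That subtracting placebo would isolate the dose step, or turn 75/1.5 and 25/5 into clean atomoxetine and oxybutynin steps.** It would not. No arm stays on 25/1.5, so longer time on active drug remains mixed with the dose change.
- **That the plan lacks component information on ODI.** SAP 4.9.3 already compares 75/5 with 25/5 and with 75/1.5 between randomized arms over the treatment nights. Within-person component steps would be an optional addition.

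**Conclusion.** The point holds as an inexpensive improvement to an exploratory analysis. The contrast as written cannot separate the dose step from non-drug change over time, and the concurrent placebo data that would remove that change are not used. The primary result and the ranked sequence are untouched.

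The size and direction of the bias are unknown. The range runs from about 3-5 points of false responder gain (10% downward drift, run-in ratio 0.80-0.90) to about 19-21 points (20% downward drift, run-in ratio 0.65). It rests on a between-person log SD of 0.30 and a night-to-night log SD of 0.25-0.35, none of which the documents give. With no drift there is no such gain.

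**What to change.** In SAP 4.9.4:

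1. Report ODI responder percentages by window for all four arms as description. Drop the odds ratio test and p-value from the within-75/5 comparison.
2. For inference, take each participant's mean ODI over the run-in nights and over the treatment nights, and form the change in log mean ODI, with a stated small offset for zeros. Estimate the 75/5-minus-placebo difference in that change with a 95% interval. Adjust for baseline log ODI by ANCOVA on the change. If a two-window mixed model is used instead, include a baseline-by-window term; without one, baseline drops out of the change contrast when data are complete.
3. Optionally report the same change for 75/1.5 and 25/5, labelled exploratory.
4. State that placebo subtraction removes non-drug drift but does not separate the dose step from longer time on active drug. Contrasts of change among the active arms share time on drug and partly address this.
5. Keep the second comparison, pooled active against placebo in the run-in, as written.

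The cost is SAP wording and one model on data already collected. The interval will be wider: with equal variances and arm sizes, the standard error of a two-arm difference is √2, or about 1.4 times, the one-arm value. A continuous measure takes the place of the responder test.

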4.10 Safety Evaluation

All safety summaries and analyses will be based upon the safety population as defined in [Section 4.4](#).

4.10.1 Adverse Events

AEs will be coded using MedDRA. The final version used will be designated in the clinical study report. For each AE, the severity level of the event (mild, moderate, or severe) will be determined by Investigator opinion.

Summary information including the number and percentage of subjects for treatment and overall by SOC and PT will be tabulated for:

- All AEs
- Pre-Treatment AE
- All AEs causally related (Related or Possibly related) to study treatment (as determined by the reporting investigator e.g. Not Related, unlikely related, possibly related, related)
- All SAEs
- All SAEs causally related (Related or Possibly related) to study treatment (as determined by the reporting investigator)
- All SUSARs
- All TEAEs
- All TEAEs causally related (Related or Possibly related) to study treatment (as determined by the reporting investigator)
- AEs that lead to discontinuation of study treatment
- All adverse events of special interest (AESI)
- TEAEs leading to death
- AEs by severity
- TEAEs by severity

A Pre-treatment AE will be defined as any AE with an onset date before the date of first administration of study treatment.

Adverse event summaries will be ordered in terms of decreasing frequency for SOC, and PT within SOC.

For each subject and each adverse event, the worst severity recorded will be attributed and used in the by-severity summaries. Similarly, the worst causality (most related to treatment) will be attributed and used in the by-causality summaries. If severity or causality is missing, the worst case will be assumed.

A by-subject listing of all adverse events will be provided. This listing will be presented by treatment group and will include: center, subject identifier, age, sex, race, adverse event (SOC, PT, and verbatim term), date of onset, date of resolution, duration, severity, seriousness, action taken, outcome and causality.

A summary of the number of subjects with TEAE outcome into “Not recovered/Not resolved”, “Recovered/Resolved”, “Recovered/Resolved with sequelae”, “Recovering/Resolving”, “Fatal”, and “Unknown” categories for number of events by treatment group and overall will be provided.

Death will be summarized by cause of death by the number and percentage of subjects experiencing events by treatment group and overall. Death data will also be listed. Patients who experienced a SAE will be listed.

Imputation of partial dates

AE start date

- If year is missing (or completely missing), do not impute.
- If (year is present and month and day are missing) or (year and day are present and month is missing), impute as January 1st.
- If year and month are present and day is missing, impute day as first day of the month.

AE end date

- If year is missing (or completely missing), do not impute.
- If (year is present and month and day are missing) or (year and day are present and month is missing), impute as December 31st.
- If year and month are present and day is missing, impute day as last day of the month.
- When the patient has died in the same month/year of partial stop date, use date of death.

In addition, for AEs, if for a partial start date, the AE start date could (when also considering the AE end date) potentially be on the first dose of study treatment date, the AE start date will be imputed with the first dose of study treatment date to assume a “worst case” scenario; e.g. AE from UNK-Jun-2017 to 23-Jul-2017 with the first dose of study treatment date 21-Jun-2017, then the AE start date will be imputed to 21-Jun-2017.

4.10.2 Clinical Laboratory Evaluation

An absolute value change from baseline and percentage change from baseline for all continuous hematology, serum chemistry and urinalysis laboratory parameter will be

summarized by analysis visit and treatment group, including scheduled and unscheduled assessment on-study period which spans the time drug is administered until the day of the patient's last contact date within the study, will be provided.

All laboratory test results will be listed by subject and study time point including changes from baseline (with the exception of urinalysis).

A separate listing will contain only values outside of normal ranges.

The number and percent of patients with clinically relevant abnormal laboratory findings will be tabulated by treatment group. The abnormal values will be flagged with 'L' for values below the lower limit of the clinical reference range and 'H' for values above the upper limit of the clinical reference range and included in the listings. The Investigator will assess whether the values outside the clinical reference range are clinically significant and these will be reported as abnormal not clinically significant (NCS) or abnormal clinically significant (CS). Clinically significant laboratory values will be recorded by the Investigator as AEs.

Shift tables from baseline for the following category will also be provided.

- Hematology: Hemoglobin, Platelet Count, RBC Count, White Cells Count
- Serum chemistry: Albumin, ALT, AST, Creatinine, Alkaline phosphatase, Potassium, Calcium, Sodium, Bilirubin, Total cholesterol, Glucose, Protein, Uric acid, Bicarbonate

For all other lab tests listing will be provided.

4.10.3 Vital Signs, Physical Findings and Other Observations Related to Safety

Vital Signs

The following vital signs measurements will be obtained:

- Systolic blood pressure (SBP) [mmHg].
- Diastolic blood pressure (DBP) [mmHg].
- Pulse rate (bpm).
- Body temperature (oral) [°C].
- Respiratory rate.

Vital signs data will be listed by subject including changes from baseline. The baseline for the vital signs measurements will be the measurement at screening.

Absolute values and changes from baseline will be presented by study visit and treatment group.

Participants who experience systolic blood pressure ≥ 160 , or diastolic blood pressure ≥ 100 , or heart rate ≥ 120 beats per minute will be tabulated separately. If triplicate vital signs are taken at a time point, the average value of the three measurements will be used for the above cutoffs.

Shift tables from baseline for the following category will also be provided.

- Systolic blood pressure (SBP) [mmHg].

- Diastolic blood pressure (DBP) [mmHg].
- Pulse rate (bpm).

12-Lead ECG

The following ECG parameters will be recorded:

- PR-interval (msec).
- QRS-interval (msec).
- QT-interval (msec).
- QTcF-interval (msec).
- Heart rate (HR) (beats per minute [bpm]).

The ECG will be evaluated by the Investigator as ‘Normal’, ‘Abnormal, NCS’ or ‘Abnormal, CS’.

All ECG parameters will be listed by subject for each study visit and treatment group including changes from baseline. The baseline for the ECG measurements will be obtained at screening.

Descriptive statistics (n, mean, SD, median, minimum, maximum) for absolute values and changes from baseline will be presented by study visit and treatment group.

A categorical summary for change from baseline for QT and QTcF interval (msec) will also be provided.

Physical Examination

Physical examination findings will be summarized by body system for each treatment group at screening/baseline.

All individual physical examination findings will be listed.

Pregnancy test

Positive pregnancy test results will be listed only.

